11.2.6 Analysis of Secondary Endpoint

In order to compare the mean change in pain score after an elapsed time of 4 hours using the active device to the mean change in pain score after an elapsed time of 4 hours using the control/sham device, the analyses as described in section 10.2.5 for the primary endpoint shall be followed.

11.2.7 Analysis of Exploratory Endpoints

In order to compare the proportion of subjects who report mild or no symptoms after an elapsed time of 2 hours using the active device to the corresponding proportion using the control/sham device, subjects will be stratified into two categories within each study arm, using the baseline pain score (6-7 vs. 8-10) as the basis for stratification. Within each of the two strata, the number of subjects with a pain score of ≤ 3 after 2 hours and the number of subjects with a pain score of > 3 after 2 hours shall be tabulated for both the active device and for the

control/sham device; results for each stratum shall be displayed in a 2 x 2 table. A Cochran-Mantel-Haenszel test shall be conducted to test the hypothesis of lack of association between the proportion of subjects reporting mild or no symptoms after 2 hours and the type of device, across all strata. An estimate of the pooled odds ratio and the associated exact 95% confidence interval will be computed, along with the p -value associated with the test of the null hypothesis.

The procedures described above shall also be conducted in order to compare the proportion of subjects who require abortive medication to control their migraine headache within 8 hours between the two device types, and to compare the proportion of subjects who report sensitivity to light after elapsed times of 2 hours and 4 hours between the two device types.

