4.3 Exploratory Endpoints

Exploratory endpoint variables are:

- The proportion of subjects who report mild or no symptoms (defined as a pain score of 3 or less) after an elapsed time of 2 hours following application of the device, with respect to their first severe or very severe migraine headache;
- The proportion of subjects who require abortive medication to control their first severe or very severe migraine headache within 8 hours following application of the device; and
- The proportion of subjects who report sensitivity to light after elapsed times of 2 hours and 4 hours following application of the device, with respect to their first severe or very severe migraine headache.

5. Inclusion/Exclusion Criteria

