5.1 Inclusion Criteria

All enrolled patients must meet all of the following inclusion criteria:

- Subject is 18 years or older;
- Subject is willing and able to provide written informed consent;
- Diagnosis of migraine, based on a history of at least 5 attacks per month with the following primary headache characteristics:
 - Headache attacks lasting 4-72 hours (untreated or unsuccessfully treated);
 - Headache has at least two of the following characteristics:
 - unilateral location;
 - pulsating quality;
 - moderate or severe pain intensity;
 - aggravation by or causing avoidance of routine physical activity (*e.g.* walking or climbing stairs);
 - Headache occurs with at least one of the following symptoms:
 - nausea and/or vomiting;
 - photophobia and phonophobia;
- Subject has experienced at least 4 migraine attacks in the last month, with at least two migraine attacks resulting in severe pain prior to the use of any abortive medications;
- Migraines are not attributed to another disorder.

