6.2 Enrollment and Randomization of Study Subjects

Subjects will be asked to provide demographic information (date of birth, gender, race/ethnicity) and relevant medical history related to migraine headaches. Subjects who meet all inclusion criteria and none of the exclusion criteria, and who provide written informed consent, will be enrolled in the study. Enrolled subjects will then be randomized to the Avulux® study glasses vs. control/sham study arm, with allocation on a 1:1 basis; subjects will be provided with the device specific to their assigned study arm. Subjects will be blinded to the type of device being assessed (both the blocking abilities when worn).

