6.4 Procedures and Assessments

Subjects will be directed to:

- apply the study glasses at the first onset of aura, or as soon as possible once they experience symptoms consistent with the onset of a migraine attack.
- avoid taking abortive medication for the first four hours of a migraine attack. If abortive medications cannot be avoided, the subject should document use.
- record the following information for the first (and all subsequent) severe or very severe migraine headaches that they experience while enrolled in the study:
 - The date and time of symptom onset;

¹ Kwong WJ and Pathak DS. Validation of the eleven-point pain scale in the measurement of migraine headache pain. *Cephalgia* 2007; 27: 336-342.

- The pain score (as assessed on the 11-point pain scale) just prior to the application of the study glasses (score needs to be greater than or equal to 6 to qualify as a severe or very severe headache);
- The time at which the study glasses are applied;
- Whether the subject was wearing prescription eyewear in addition to the study glasses, or whether the study glasses alone were worn;
- The pain score (as assessed on the eleven-point pain scale) 2 hours after the study glasses are applied;
- The pain score (as assessed on the eleven-point pain scale) 4 hours after the study glasses are applied;
- The type of abortive medication taken (if any) to control headache symptoms, the dosage taken, and the time at which the medication is taken; and
- Any experience of light sensitivity within 4 hours after the study glasses are applied, and the time at which light sensitivity is first experienced.

Subjects will participate in the study for a maximum of four (4) weeks \pm 3 days after enrollment; if a given subject does not experience a severe or very severe migraine headache within four (4) weeks, that subject will not be included in the evaluable study population.

Study coordinators will contact subjects once per week to ensure they are wearing the study device as instructed, and that they are recording the requested information related to their headaches. These weekly contacts will also enable coordinators to identify and address any barriers to adherence with the protocol.

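### Light sensitivity is not recorded just before the glasses go on, so its exploratory comparison loses precision and cannot tell relief from prevention

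*Combined protocol and SAP*

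**What the plan says.** - **Endpoint.** Section 4.3 defines it as "The proportion of subjects who report sensitivity to light after elapsed times of 2 hours and 4 hours following application of the device", for the first severe or very severe headache. It does not depend on whether the symptom was present at application.
- **Data collected.** In section 6.4 the only symptom measure taken "just prior to the application of the study glasses" is the pain score. The light-sensitivity item reads "Any experience of light sensitivity within 4 hours after the study glasses are applied, and the time at which light sensitivity is first experienced". At enrolment, section 6.2 collects "relevant medical history related to migraine headaches", which says nothing about the state of the analysed attack.
- **Eligibility.** Section 5.1 has "Headache occurs with at least one of the following symptoms": nausea and/or vomiting is one option, and photophobia together with phonophobia is the other. Photophobia is therefore not required.
- **Analysis.** Section 11.2.7 builds a CMH test for the pain-response endpoint, "using the baseline pain score (6-7 vs. 8-10) as the basis for stratification", and reuses the same procedure for abortive medication "and to compare the proportion of subjects who report sensitivity to light after elapsed times of 2 hours and 4 hours". No section names a light-sensitivity baseline, stratum or subset. Section 11.2.1 assigns exploratory endpoints to the per-protocol population.

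**The concern.** Section 2 attributes the device's action to blocking light suspected of stimulating photophobic responses, so this endpoint lies closest to the proposed mechanism. For pain, the plan uses the pre-application value throughout: in the change score, in the baseline comparison and as a stratifier. Light sensitivity has no counterpart.

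A subject without light sensitivity at 2 hours may have been relieved or may never have had it in that attack. A subject with it may have had it all along or may have developed it under the glasses. The planned data cannot sort these cases, and the analysis cannot adjust for a pre-application status that was never recorded. The SAP wording can still change until database lock, but a baseline that was not collected cannot be recovered.

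**Working it through.** **The plan's own figure.** Section 11.1 gives 27 per arm for 95% power on the primary endpoint (difference 2, SD 2.0, two-sided 0.05). The noncentral t calculation gives power 0.942 at 26 and 0.9501 at 27, so 27 reproduces. Then 27/0.8 = 33.75, rounded up to 34 per arm, or 68 in total. No figure is given for light sensitivity. I use 27 per arm below; the per-protocol number may differ.

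**Assumed inputs (none is in the documents).** q is the share light-sensitive at application, s the proportion of these still sensitive at 2 hours (0.50 active, 0.80 sham), and o the proportion of the others with new onset.

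**Why relief and prevention cannot be separated.** Each arm shows one proportion, p = q·s + (1 − q)·o, with three unknowns. Take q = 0.75:
- Onset 0.05 in both arms: sham 0.75 × 0.80 + 0.25 × 0.05 = 0.6125; active 0.75 × 0.50 + 0.25 × 0.05 = 0.3875; difference 0.225, all of it relief.
- Onset 0.50 sham, 0.25 active: sham 0.60 + 0.125 = 0.725; active 0.375 + 0.0625 = 0.4375; difference 0.2875, of which 0.225 is relief and 0.0625 prevention.

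The second pair of proportions would also arise if every subject were sensitive at application and 0.725 versus 0.4375 stayed so. The planned data could not tell these two situations apart.

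**Chance imbalance.** The SD of the between-arm difference in q is √(2q(1 − q)/27): 0.082 at q = 0.9, 0.118 at 0.75 and 0.133 at 0.6. The exact binomial probability of an imbalance of at least 10 points is 0.25 at q = 0.9, 0.39 at 0.8 and 0.49 at 0.6.

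**Validity.** With no device effect, simulated type I error is about 0.04 to 0.05 whether the CMH test is stratified by pain or by pre-application light sensitivity.

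**Power.** Simulated CMH test, no continuity correction, 27 per arm, pain stratum unrelated to light sensitivity:

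| q | Onset active / sham | Planned stratifier | Pre-application status | Gain (points) |
|---|---|---|---|---|
| 0.90 | 5% / 5% | 0.50 | 0.58 | 8 |
| 0.75 | 5% / 5% | 0.37 | 0.50 | 13 |
| 0.60 | 5% / 5% | 0.25 | 0.38 | 13 |
| 0.90 | 10% / 10% | 0.52 | 0.59 | 7 |
| 0.80 | 10% / 10% | 0.41 | 0.51 | 10 |
| 0.60 | 10% / 10% | 0.26 | 0.35 | 9 |
| 0.75 | 30% / 30% | 0.36* | 0.42 | 6 |
| 0.75 | 25% / 50% | 0.56* | 0.60 | 4 |
| 0.75 | 30% / 60% | 0.62* | 0.63 | 1 |

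*Comparator without strata. A pain stratum unrelated to light sensitivity barely changes power: at q = 0.8 with 10% onset it is 0.42 without strata and 0.41 with the pain stratum.

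A separate set of runs against the pain-stratified test gave 0.36 to 0.48 at q = 0.75 and 0.25 to 0.39 at q = 0.60 (5% onset), and gains of about 3 to 5 points when onset was common or prevented. Differences of a point or two between runs are simulation error.

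**The case against.** - **The endpoint is exploratory.** It is not powered, and at q = 0.75 with 5% onset power is only about 50% even after the change. This stands and limits the weight of the point.
- **Randomisation already covers chance imbalance.** A reader might infer that a lower rate in one arm could be an artefact of baseline imbalance and that the comparison is therefore biased. The documents do not support that: allocation is randomised 1:1, and the test holds its error rate. Imbalance costs precision only.
- **Subjects without the symptom belong in the comparison.** A reader might infer that they merely dilute the endpoint. However, section 3.3 asks about the proportion suffering from light sensitivity, not the proportion relieved. Section 2 says the filtered light may trigger some migraines, and section 6.4 asks for application as early as possible. Prevention is thus a plausible effect, and these subjects should stay in the analysis.
- **The gain depends on unknown rates.** Low onset, equal in both arms, favours the change; the lower rows of the table do not. If light sensitivity tracks pain, the existing strata recover part of the precision, and the documents do not give that correlation.
- **The time of first experience might serve as a baseline.** Occasionally it may precede application, but the item is framed for the 4 hours afterwards ("Any experience of light sensitivity within 4 hours after the study glasses are applied"), so it is not a dependable measure.
- **A baseline item alone is not enough.** The diary records any experience and its first time, not status at 2 and 4 hours. The outcome itself cannot be derived until that is added. This stands, and the fix below includes it.

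**Conclusion.** The gap is real and follows directly from sections 4.3, 5.1, 6.4 and 11.2.7. Its consequences are lower precision and a result that cannot separate relief from prevention; it is not a threat to validity. With 60-90% sensitive at application, persistence of 50% versus 80%, and 27 per arm, adjustment is worth about 3 to 14 points of power over the pain-stratified test. The gain falls to about 1 point in the strongest prevention setting examined. All these rates are assumptions, so the power gain is illustrative; the interpretability gap does not depend on them. It would be wrong to conclude that the light-sensitivity test is biased, or that the primary or secondary conclusions are affected. This is a cheap improvement.

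**What to change.** 1. **Section 6.4:** add a yes/no item for light sensitivity just before the glasses are applied, beside the pain score already taken then, and yes/no status at 2 hours and at 4 hours.
2. **Section 11.2.7:** stratify the light-sensitivity CMH test by the pre-application item, alone or crossed with baseline pain. Crossing thins the strata: at q = 0.9, 54 × 0.1 = 5.4 subjects are not sensitive, or about 2.7 per pain stratum if pain splits evenly.
3. Keep all subjects of the planned population in the main comparison, whatever their pre-application status.
4. Report descriptively, by arm, the proportion free of light sensitivity at 2 and 4 hours among those sensitive at application, and the proportion with onset among those not. Both groups are defined before the device is worn.

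**Cost:** three tick boxes per headache, a small extra burden during an attack, and a few lines of SAP text. The diary change must be made before data are collected. Sample size and the primary and secondary analyses are unchanged.

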11.2.8 Blinding Assessment

As described in section 5.4, subjects who complete all study procedures will be asked at the final site visit to provide an opinion as to which type of device they believe they were assigned to (Avulux® vs. control/sham vs. do not know). Blinding assessments shall be performed on the resulting data, following procedures as described in James *et al.*⁵ and in Bang *et al.*⁶

11.2.9 Adverse Event Data

Analyses of adverse event data shall be conducted with respect to all enrolled subjects who participated in the use of either the active device or the control/sham device during study procedures.

For each study device, the number of adverse events (AEs) shall be tabulated, and descriptive statistics shall be utilized to summarize the severity of AEs and their relationship to study procedures for each device.

All serious adverse events (SAEs) will be listed individually.

⁵ James KE, Bloch DA, Lee KK *et al.* An index for assessing blindness in a multi-centre clinical trial: disulfiram for alcohol cessation – a VA cooperative study. *Stat Med* 1996, 15: 1421-1434.

⁶ Bang H, Ni L and Davis CE. Assessment of blinding in clinical trials. *Control Clin Trials* 2004, 25: 143-156.
